## 1.1 Schedule of Assessments and Procedures

**Table 1-1 Schedule of Assessments and Procedures**

Study Visit	SCR	Visit 1	Visit 2	Visit 3	Visit 4	Visit 5	Visit 6	Visit 7	Visit 8	Visit 9	Visit 10	Visit 11	Visit 12	Visit 13 Study End	UNSCH /ET
Study Day (Visit Window)	Day -14 to Day -1	Day 1	Day 8 ( $\pm 1$ Day)	Day 15 ( $\pm 1$ Day)	Day 22 ( $\pm 3$ Days)	Day 29 ( $\pm 2$ Days)	Day 43 ( $\pm 2$ Days)	Day 76 ( $\pm 3$ Days)	Day 90 ( $\pm 14$ Days)	Day 120 ( $\pm 3$ Days)	Day 150 ( $\pm 3$ Days)	Day 181 ( $\pm 14$ Days)	Day 273 ( $\pm 14$ Days)	Day 365 ( $\pm 14$ Days)	
Procedures															
Informed consent	X														
Eligibility	X	X			X										
Medical history	X	X a	X a	X a	X a	X a	X a		X a			X a	X a	X a	
Demographic and baseline characteristics b	X														
Complete physical examination	X														
Targeted physical examination c		X	X	X	X	X	X						X		X
Height, weight, BMI	X														
Vital sign measurements d	X	X d	X	X	X d	X	X		X			X	X	X	X
Urine pregnancy test e	X	X			X										
Urine drug screen f	X														
HIV-1/2, HBsAg, HCV g	X														
Nasopharyngeal swab for RT-PCR h	X			X											X
Serostatus (IgM & IgG) for SARS-CoV-2 q	X														
Oral Temperature (pre-vaccination)		X			X										

CONFIDENTIAL

Study Visit	SCR	Visit 1	Visit 2	Visit 3	Visit 4	Visit 5	Visit 6	Visit 7	Visit 8	Visit 9	Visit 10	Visit 11	Visit 12	Visit 13 Study End	UNSCH /ET
Study Day (Visit Window)	Day -14 to Day -1		Day 8 (±1 Day)	Day 15 (±1 Day)	Day 22 (±3 Days)	Day 29 (±2 Days)	Day 43 (±2 Days)	Day 76 (±3 Days)	Day 90 (±14 Days)	Day 120 (±3 Days)	Day 150 (±3 Days)	Day 181 (±14 Days)	Day 273 (±14 Days)	Day 365 (±14 Days)	
Procedures															
Vaccination dose (IM)		X			X										
60 minute post-vaccination monitoring (arm check, VS, and targeted PE if general symptoms present)		X			X										
Distribution and training on Diary Card completion		X			X										
Review of Diary Card i			X			X									
Telephone visit j								X		X	X				
SARS-CoV-2 exposure and asymptomatic monitoring k															
Adverse events l															X
SAEs, MAAEs, NOCDs and AESIs m															X
Prior and concomitant medications n															X
Clinical safety laboratory tests o	X		X	X	X		X					X			X
Blood collection for ELISA IgM and IgG total antibodies p	X		X	X	X	X	X		X			X	X	X	X

CONFIDENTIAL

Study Visit	SCR	Visit 1	Visit 2	Visit 3	Visit 4	Visit 5	Visit 6	Visit 7	Visit 8	Visit 9	Visit 10	Visit 11	Visit 12	Visit 13 Study End	UN SCH /ET
Study Day (Visit Window)	Day -14 to Day -1		Day 8 (±1 Day)	Day 15 (±1 Day)	Day 22 (±3 Days)	Day 29 (±2 Days)	Day 43 (±2 Days)	Day 76 (±3 Days)	Day 90 (±14 Days)	Day 120 (±3 Days)	Day 150 (±3 Days)	Day 181 (±14 Days)	Day 273 (±14 Days)	Day 365 (±14 Days)	
Procedures															
Blood collection for neutralizing, anti-RBD, and anti-Fc antibodies	X		X	X	X	X	X		X			X	X	X	X
Cell-mediated immunity (PBMC)	X		X		X	X	X		X			X	X	X	X
PBMC and serum sample collection for future research	X		X		X	X	X		X			X	X	X	X

Abbreviations: AE = adverse event; AESI = adverse event of special interest; BMI = body mass index; CRU = clinical research unit; ELISA = enzyme-linked immunosorbent assay; ET = Early Termination visit; HBsAg = hepatitis B surface antigen; HCV = hepatitis C virus; HIV = human immunodeficiency virus; Ig = immunoglobulin; IM = intramuscular; MAAE = medically attended adverse event; NOCD = new-onset chronic disease; PBMC = peripheral blood mononuclear cells; PE = physical examination; RBD = receptor binding domain; RT-PCR = reverse transcription polymerase chain reaction; SAE = serious adverse event; SCR = Screening visit; UNSCH = Unscheduled visit; VS = vital signs

- Medical history will be collected to determine if any changes have occurred since last visit.
- Baseline characteristics include tobacco use and history.
- Post vaccination targeted physical examination includes evaluation of any system indicated by an AE complaint.
- Pre-dose and approximately 60 minutes post vaccination. Vital signs will be measured after the subject has been resting quietly in a seated position for at least 5 minutes. Vital signs measurements will include blood pressure, heart rate, respiratory rate, and oral temperature.
- A negative urine pregnancy test must be documented before vaccination on Day 1 and Day 22 for women of childbearing potential. A serum pregnancy test must be performed to confirm any positive urine pregnancy test.
- For Parts A and B, a positive urine drug screen without evidence of corresponding prescribed concomitant medication(s) at Screening is exclusionary. A positive drug screen result with a corresponding prescribed concomitant medication will be allowed if, in the opinion of the Investigator and Medical Monitor, the concomitant medication does not make the subject unsuitable to participate in the clinical trial.
- Not performed for Part C.
- Serial nasopharyngeal swabs (RT-PCR) will be performed on subjects that report either potential exposure to SARS-CoV-2 (ie, close contact tests positive for SARS-CoV-2) or symptoms of SARS-CoV-2 infection. Testing will occur every 2 weeks for a total of 4 weeks (if 2 consecutive negative tests) or until negative after a positive result. Positive results will be reported as an AESI ([Section 8.2.2](#)) and subjects followed for disease severity, duration, and outcome.

CONFIDENTIAL

- i. Review of Diary Card ([Appendix A](#)) will include a check that the Diary Card has been completed appropriately and re-training the subjects, if necessary. Any illogical entries will be queried by the site and corrected if appropriate.
- j. During telephone visits, CRU staff will interview the subjects about any potential exposure to the virus. If a subject has had potential exposure, the CRU will ask the subject to come in for an unscheduled visit which will include a nasopharyngeal swab. Subjects will be reminded to contact the clinical site any time there is potential exposure to SARS-CoV-2.
- k. Subjects will be monitored for SARS-CoV-2 exposure for potential asymptomatic infection throughout the study. CRU staff will interview subjects about any potential exposure to the virus. If a subject has had potential exposure, the CRU will perform an unscheduled nasopharyngeal swab.
- l. Adverse events include questioning regarding the specifically elicited events on the Diary Card and complaints spontaneously reported in response to nondirective questions.
- m. SAEs, MAAEs, NOCDs, and AESIs will be collected from Day 1 through Day 365/approximately 1 year after first vaccination.
- n. Includes all medications taken during the first 43 days of the study, including those started 30 days before and ongoing at vaccination.
- o. Refer to [Table 7-1](#) for a detailed list of clinical laboratory test parameters. Clinical laboratory tests can be repeated once at screening to confirm an out-of-range result. If Part C Expansion (optional) is performed, safety laboratory tests will be performed at screening for all Part C subjects in order to satisfy the inclusion/exclusion criteria. In addition, the first 200 subject in Part C will have safety laboratory tests performed at all time points. The remaining subjects in Part C will not have safety laboratory tests performed at any of the post-dose time points unless the Investigator deems it necessary.
- p. Subjects with positive ELISA anti-N IgG results without COVID-19 symptoms may indicate asymptomatic SARS-CoV-2 infection and will be followed appropriately. Subjects with a positive ELISA anti-N IgG result should have a PCR test and be followed until both are negative as in the protocol instructions ([Section 7.6](#)).
- q. Serostatus will not be used to determine eligibility; however, subjects with a positive serostatus for SARS-CoV-2 will have safety and efficacy subgroup analysis performed.

NOTE: In the event multiple post-dose procedures are required to be conducted at the same nominal time point, the timing of antibody titer and cellular immunity blood sample collections will take priority over all other scheduled activities. In practice, the following order is recommended: (1) vital signs measurements; (2) antibody titer and cellular immunity blood sampling; (3) clinical laboratory tests sampling; (4) physical examination and height and body weight measurements. Vital signs may be conducted up to 10 minutes, prior to the nominal time to minimize the potential autonomic effects of blood draws on these measurements and remaining assessments (eg, clinical laboratory tests sampling, physical examination, and height and body weight measurements) may be performed after the nominal time point.

CONFIDENTIAL

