### **3 OBJECTIVES AND ENDPOINTS**

#### **3.1 Objectives**

##### **3.1.1 Primary Objective**

To assess the safety and reactogenicity of two doses of TAP-COVID-19 vaccine with CpG adjuvant for 7 days post vaccination compared with placebo as determined by solicited local and systemic reactogenicity

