Both Part A (18-49 years) and Part B (50-85 years) will be randomized in a 2:1 ratio (active:placebo) for each treatment dose (15 µg and 45 µg TAP-COVID-19 vaccine + 0.5 mg CpG) for a total of 90 subjects per Part (30 subjects 15 µg TAP-COVID-19 vaccine + 0.5 mg CpG:30 subjects 45 µg TAP-COVID-19 vaccine + 0.5 mg CpG:30 subjects placebo).

Treatment A: TAP-COVID-19 vaccine (15 µg) + CpG (0.5 mg) IM injection on  
Day 1 and Day 22 ( $\pm 3$  days)

CONFIDENTIAL

Treatment B: TAP-COVID-19 vaccine (45 µg) + CpG (0.5 mg) IM injection on Day 1 and Day 22 ( $\pm 3$  days)

Treatment C: Placebo (buffered saline solution) IM injection on Day 1 and Day 22 ( $\pm 3$  days)

Study vaccine will be prepared by an unblinded site pharmacist and administered at the clinical research site on Day 1 and Day 22 ( $\pm 3$  days) by unblinded CRU personnel. Subjects will be observed for immediate AEs and/or reactogenicity for approximately 60 minutes after administration of vaccine. Subjects will be provided with a Diary Card and will be trained to record specifically elicited systemic and local symptoms daily as well as any additional AEs during the 7-day follow-up period after each vaccination. Visits will be conducted at the clinical site on an outpatient basis or as a telephone visit per the Schedule of Assessments and Procedures ([Table 1-1](#)). Subjects will participate in the study for approximately 1 year from the first dose.

AEs and concomitant medications will be captured through Day 43. Blood and serum samples for safety laboratory tests, RBD IgG and IgM antibodies, and neutralizing antibody titers, cell-mediated immunity, and other future biomedical research will be obtained at baseline and before administration of vaccine dose 2 and after each vaccination per the Schedule of Assessments and Procedures ([Table 1-1](#)). SAEs, MAAEs, NOCDs, and AESIs only will be captured after Day 43 to study completion (Day 365 [approximately 1 year after vaccination]).

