#### **4.1.1 Duration of Study**

Each subject will receive two doses of study vaccine or placebo, the first on Day 1 and the second on Day 22 ( $\pm 3$  days). The total duration of subject participation is approximately 1 year (including screening, treatment, and follow-up periods).

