## **5.7      Independent Safety Review Committee, Study Stopping Rules, and Study Termination**

### **5.7.1      Independent Safety Review Committee**

A safety review will be performed by the iSRC according to details established at the start of the study and provided in the iSRC charter. The Investigator will provide a brief summary to the iSRC of any pertinent safety events prior to the iSRC meeting. The three member iSRC will consist of, at a minimum, two physicians with experience in vaccines and one statistician.

The iSRC will review the safety and tolerability data through Day 8 for each of the sentinel subject groups prior to the enrollment of the remaining cohort subjects. In the event that iSRC has not met for the post Day 8 review because the entire sentinel group (n = 3) has not completed Day 8 before a sentinel subject is to receive the second vaccine on Day 22, the iSRC will meet on an ad hoc basis, to ensure there are no safety concerns and that none of the Individual Discontinuation Criteria ([Section 5.5](#)) or Study Halting Rules ([Section 5.7.2](#)) have been met, prior to the sentinel subjects receiving the second vaccine.

The iSRC will be convened to review all available safety data including solicited AEs, unsolicited AEs, SAEs, MAAEs, NOCDs, AESIs, vitals, safety laboratory, and physical exams results of Part A low dose when all subjects have received the first vaccination and have all safety data through Day 8. If there are no safety concerns after the iSRC meeting, study enrollment will continue to Part A high dose and Part B low dose. The same strategy will be used to move from Part B low dose to Part B high dose.

The iSRC will also meet when a minimum of 23 subjects have completed Day 29 after the second vaccination for Part A (high and low dose) and for Part B (high and low dose) to review safety data to ensure that there are no concerns.

The iSRC will be asked to review unblinded immunogenicity and safety data when the first 30 subjects vaccinated in the Part A low dose group (including active and placebo subjects) have data available from Day 1 through Day 43 for an assessment of the risk-benefit of the trial. For the

CONFIDENTIAL

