## **5.7.2                    Study Halting Rules**

The occurrence and confirmation of 1 or more of the following findings will result in suspension of further enrollment and study vaccine administration pending urgent review (within 1 week) of the safety data by the iSRC. Subjects who are withdrawn from study vaccine (if applicable) will continue to be monitored ([Section 5.6](#)) for safety and immunogenicity.

1. One or more subjects experience an SAE assessed as possibly related, probably related, or related to study vaccine without a plausible alternative explanation.

CONFIDENTIAL

2. One or more subjects have generalized urticaria during the 7-day post vaccination period.
3. One or more subjects develop a Grade 4 local reaction for which there is no alternative plausible explanation.
4. One or more subjects experiences laryngospasm, bronchospasm, or anaphylaxis after vaccine administration considered related to the vaccine.
5. One or more subjects develop a fever  $>40^{\circ}\text{C}/104^{\circ}\text{F}$  during the 7 days post vaccination period that is assessed as possibly related, probably related, or related to study vaccine without a plausible alternative explanation.
6. Two or more subjects within an individual treatment group, or 2 or more subjects across treatment groups, experience any Grade 3 or higher abnormality in the same laboratory parameter determined by the Investigator or medical monitor as clinically significant and that are assessed as possibly related, probably related, or related to study vaccine without a plausible alternative explanation.

Note: An unblinded statistician or designee will assist with determining whether stopping rule #6 is met.

7. Two or more subjects across treatment groups experience a Grade 3 or higher AE, MAAE, or AESI of the same or similar preferred terms (as categorized by MedDRA) assessed as possibly related, probably related, or related to study vaccine without a plausible alternative explanation.
8. Any subject with severe SARS-CoV-2 infection will be assessed for the possibility of vaccine-associated enhanced respiratory disease. Severe SARS-CoV-2 infection is defined as individuals who have virologically confirmed SARS-CoV-2 infection with any of the following:

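### The first scheduled safety laboratory panel after dose 2 comes 16 to 26 days later, so a silent, short-lived dose-2 abnormality is missed unless the Investigator orders an unscheduled test

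*Combined protocol and SAP*

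**What the plan says.** Section 4.1.1 gives two doses, "the first on Day 1 and the second on Day 22", the second with a window of ±3 days. Table 1-1 marks "Clinical safety laboratory tests" at Screening, Days 8, 15, 22, 43 and 181 and in the unscheduled/early-termination column. The Day 29 cell is blank in both the clean and the tracked-changes copies of protocol version 9.0, so a shifted column is unlikely. In the same table "Blood collection for neutralizing, anti-RBD, and anti-Fc antibodies" is marked at Day 29, as are the ELISA and PBMC samples.

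Section 4.1 says that blood samples "will be obtained at baseline and before administration of vaccine dose 2 and after each vaccination per the Schedule of Assessments and Procedures".

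Two safety mechanisms use laboratory results:

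- Halting rule 6 (Section 5.7.2) applies when two or more subjects "experience any Grade 3 or higher abnormality in the same laboratory parameter" and the finding is judged clinically significant and related.
- Section 5.7.1 adds a committee review: "The iSRC will also meet when a minimum of 23 subjects have completed Day 29 after the second vaccination".

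Section 7.7.3 lets the Investigator order further safety laboratory tests when needed. Section 4.1.2 also has the committee review all data through Day 43 for both parts and both dose levels.

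**The concern.** In a first-in-human, two-dose trial one would expect laboratory sampling after the second dose to be at least comparable with sampling after the first. Here dose 1 has three panels in roughly its first three weeks and dose 2 has one, at the end of the corresponding period. Scheduled panels exist mainly to find abnormalities that cause no symptoms, and those are the ones this gap would let through.

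Three things are at stake:

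1. **Halting rule 6.** For a dose-2 effect, no scheduled result can contribute to the rule before the Day 43 visit.
2. **The Day 29 committee review.** If Day 29 in that trigger means Visit 5, subjects who have only reached that visit bring no scheduled laboratory value from after dose 2.
3. **Interpretation.** A low laboratory-abnormality rate after dose 2 could reflect when blood was drawn rather than tolerability.

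**Working it through.** The plan states no figure for this point, so there is none to reproduce. The check is of timing.

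**Inputs.** From Table 1-1 and Section 4.1.1: dose 1 on Day 1; dose 2 on Day 22 ±3, so Days 19 to 25; panels at Day 8 ±1, Day 15 ±1, Day 22 ±3, Day 43 ±2 and Day 181 ±14; Visit 5 at Day 29 ±2. Section 4.1 says samples "will be obtained at baseline and before administration of vaccine dose 2 and after each vaccination", so the Day 22 panel precedes dose 2 and counts as a post-dose-1 result.

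**Formulas.** Days after dose 1 = visit day − 1. Days after dose 2 = visit day − dose-2 day, with both windows anchored to Day 1.

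| Visit | After dose 1 | After dose 2 |
|---|---|---|
| Day 8 panel | 7 (6 to 8) | not applicable |
| Day 15 panel | 14 (13 to 15) | not applicable |
| Day 22 panel | 21 (18 to 24) | drawn before the dose |
| Day 29, no panel | 28 (26 to 30) | 7 (29−2−25 = 2 to 29+2−19 = 12) |
| Day 43 panel | 42 (40 to 44) | 21 (43−2−25 = 16 to 43+2−19 = 26) |
| Day 181 panel | 180 (166 to 194) | 159 (142 to 176) |

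So no scheduled panel falls in the first 15 days after dose 2, and the first result a schedule can supply is from Days 41 to 45. The protocol does not say whether Day 43 is counted from Day 1 or from the actual dose-2 date. If the latter, the gap is 21 ± 2 = 19 to 23 days, and the conclusion is the same.

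**Illustration of detection.** Assumptions: onset equally likely on days 1, 2, 3 or 4 after a dose; all visit-window combinations equally likely; an abnormality is caught if a scheduled panel falls while it is present. Each range reflects whether the final day is counted as present.

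| Duration | After dose 1 | After dose 2, as planned | After dose 2, with a Day 29 panel |
|---|---|---|---|
| 3 days | 8-25% | 0% | 21-34% |
| 7 days | 92-100% | 0% | 73-83% |
| 10 days | 100% | 0% | 94-96% |
| 21 days | 100% | 76-86% | 100% |
| 28 days | 100% | 100% | 100% |

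With onset spread over days 0 to 14 instead, the 7-day figures are 89-96% after dose 1, 7-11% after dose 2, and 50-57% after dose 2 with a Day 29 panel. The contrast between doses is thus largest for abnormalities lasting roughly one to two weeks. Very brief ones are mostly missed after either dose, and those of four weeks are caught after both.

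**The committee trigger.** Read as Visit 5, its timing is 2 to 12 days after dose 2 and precedes the Day 43 panel. Read literally as 29 days after dose 2, it is about study Day 22 + 29 = 51, and the Day 43 panel would be in hand.

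**The case against.** The strongest reply is that this is a design choice with safeguards, and much of that stands.

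- A reader might infer that transient dose-2 toxicity must be missed. The documents do not support that. The row is marked for unscheduled visits, Section 7.7.3 allows extra tests, Visit 5 is on site with history, examination, vital signs and diary review, and rule 6 is not confined to scheduled results. What remains exposed is the abnormality that gives no reason to test.
- A reader might infer that the primary objective is compromised, since it begins "To assess the safety and reactogenicity of two doses of TAP-COVID-19 vaccine with CpG adjuvant". That objective goes on to specify solicited local and systemic reactions over 7 days, and the primary endpoints in Section 3.2.1 are solicited events. Laboratory values are not a listed endpoint.
- A reader might infer bias between arms. All arms share one schedule, and the comparisons in Section 3.1.2 are between arms. The protocol plans no dose-1 versus dose-2 laboratory comparison.
- A reader might infer that the committee never sees a laboratory value from after dose 2. The Day 43 review in Section 4.1.2 includes one.
- A reader might infer that the schedule contradicts Section 4.1. It does not: Day 43 is after dose 2, and that sentence defers to the schedule.
- It also cannot be claimed that a by-dose laboratory table is missing from the analysis plan. Section 9.8 leaves detail to a SAP whose text is not among the documents reviewed.

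Finally, the rationale given for Amendment 8 says enrollment has stopped, so a change to Visit 5 may reach few Part A or B subjects. That limits the remedy but does not remove the gap.

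**Conclusion.** The point holds as a limit on detection. Scheduled panels cover about 7, 14 and 21 days after dose 1 but only 16 to 26 days after dose 2 (19 to 23 if counted from the actual dose). Silent laboratory abnormalities that resolve within about two weeks of dose 2 will not appear in scheduled data.

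The intervals follow directly from Table 1-1. The detection percentages rest on assumed onset and duration and are illustrations only. It does not follow that post-dose-2 rates must look lower; that depends on how long abnormalities last. The consequence for the Day 29 committee review depends on that trigger meaning Visit 5. The matter is worth correcting because the remedy is cheap, but it does not undermine the trial's main comparisons.

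**What to change.** 1. In Table 1-1, mark the safety laboratory panel at Visit 5 (Day 29), using the existing blood draw, for any Part A or B subject not yet at that visit and for the first 200 Part C subjects. The cost is one extra tube and panel per subject, with no extra visit. Because the draw falls 2 to 12 days after dose 2, it narrows the difference from dose 1 without closing it.
2. For subjects already past Visit 5, tabulate laboratory abnormalities separately for the period after dose 1 and before dose 2, and for the period after dose 2. Show the sampling days in each, and state that no scheduled panel covered the first 15 days after dose 2. The cost is one more split in the laboratory tables and a sentence in the report; no new data are needed.

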## Part A and Part B:

Subjects will be screened up to 14 days (Day -14 to Day -1) before randomization. Overall, approximately 90 eligible healthy adults ages 18-49 years (inclusive) will be enrolled for Part A and 90 eligible healthy adults ages 50-85 years will be enrolled for Part B.

Sentinel dosing will be utilized in this FIH study. Sentinel cohorts will be used for the following groups:

- Part A (18-49 years) low dose (15 µg TAP-COVID-19 vaccine + 0.5 mg CpG)
- Part B (50-85 years) low dose (15 µg TAP-COVID-19 vaccine + 0.5 mg CpG)
- Part A (18-49 years) high dose (45 µg TAP-COVID-19 vaccine + 0.5 mg CpG)
- Part B (50-85 years) high dose (45 µg TAP-COVID-19 vaccine + 0.5 mg CpG)

Three sentinel subjects from each part will be randomized 2:1 (active:placebo). The iSRC will review the safety data for the sentinel subjects through Day 8 prior to enrollment of the remaining cohort subjects randomized 2:1 (active:placebo). In the event that iSRC has not met for the post Day 8 review because the entire sentinel group (n = 3) has not completed Day 8 before a sentinel subject is to receive the second vaccine on Day 22, the iSRC will meet on an ad hoc basis, to ensure there are no safety concerns and that none of the Individual Discontinuation Criteria ([Section 5.5](#)) or Study Halting Rules ([Section 5.7.2](#)) have been met, prior to the sentinel subjects receiving the second vaccine.

When all subjects in Part A (18-49 years) low dose have received the first vaccination and have all safety data through Day 8, the iSRC ([Section 5.7.1](#)) will convene and review the safety data to ensure that there are no safety concerns and that none of the Study Halting Rules have been met ([Section 5.7.2](#)) before recommending that the study enroll Part A high dose and Part B (50-85 years) low dose.

When all subjects in Part B (50-85 years) low dose have received the first vaccination and have all safety data through Day 8, the iSRC will convene and review the safety data to ensure that there are no safety concerns and that none of the Study Halting Rules have been met before recommending that the study enroll Part B high dose.

The iSRC will convene and review the safety data when a minimum of 23 subjects have completed Day 29 after the second vaccination for Part A (low and high dose) and for Part B (low and high dose) to ensure that there are no concerns.

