## **9 STATISTICAL CONSIDERATIONS**

The statistical analysis will be conducted following the principles as specified in ICH Topic E9 (CPMP/ICH/363/96).

All statistical analyses will be described in a separate SAP.

The statistical evaluation will be performed using SAS® software version 9.4 or higher (SAS Institute, Cary, NC). All data will be listed, and summary tables will be provided. No formal significance testing will be performed. Summary statistics will be presented by treatment group and include subset analysis (eg, all subjects, seronegative subjects [ie, neutralizing antibody titer < 10 at screening], seropositive subjects, and subjects that received an FDA Emergency Use Authorization/licensed COVID vaccine). For continuous variables, data will be summarized with the number of subjects, mean, standard deviation, median, minimum, maximum, geometric mean, CV%, GeoCV%, and 95% CI by treatment group. For categorical variables, data will be tabulated with the number and proportion of subjects for each category by treatment group.

The database will be locked and unblinded after the data have been monitored for all subjects through Day 43. Details of the unblinded interim analysis are presented in [Section 9.5](#).

The final analysis of the safety and immunogenicity data collected from Day 43 through Day 365/approximately 1 year after first vaccination will be performed after the study is completed. An addendum to the initial CSR will be prepared with data from final analysis. Details of the statistical analyses, methods, and data conventions will be described in the SAP.

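### The immunogenicity baseline is the screening draw, 1 to 14 days before dose 1, so an unrecognised infection in that gap is counted in the fold-rise and T-cell endpoints

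*Combined protocol and SAP*

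**What the plan says.** Section 4.1 sets the screening window: "Subjects will be screened up to 14 days (Day -14 to Day -1) before randomization". In Table 1-1, four rows carry a mark at screening, nothing at Visit 1 (Day 1) and the next mark at Day 8: the ELISA IgM/IgG row, "Blood collection for neutralizing, anti-RBD, and anti-Fc antibodies", the cell-mediated immunity (PBMC) row and the row for future-research samples. The row "Nasopharyngeal swab for RT-PCR" is marked at screening, Day 15 and unscheduled visits.

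The text of Section 4.1 says that samples "will be obtained at baseline and before administration of vaccine dose 2 and after each vaccination per the Schedule of Assessments and Procedures". It does not date the baseline sample, and it defers to a table in which the only draw before dose 1 is at screening. Section 9 points the same way by defining the seronegative subset by "neutralizing antibody titer < 10 at screening". Section 7.7.3 defines baseline as the last value before dose 1, but only for safety laboratory tests.

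Section 3.2.2 sets GMFR relative to baseline, and Section 3.2.3 does the same for the T-cell counts. Seroconversion in Section 3.2.2 is the proportion with detectable RBD antibody at the visit. Sections 9.2 and 9.6 analyse immunogenicity in the mITT Population, which keeps anyone dosed who provides any serology data.

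**The concern.** A baseline for a fold rise should describe the subject at the moment of vaccination. Here it may be two weeks old, and neither serology nor a swab is scheduled between that draw and dose 1. A subject who becomes infected without noticing it in the interval keeps a low baseline titre and a seronegative label. The antibody and T-cell rise that follows is then read as a response after vaccination. In an active arm it adds to the apparent vaccine response, and in the placebo arm it raises a fold change that should be close to 1. Dose 2 is treated differently: Day 22 has pre-dose titre and PBMC samples. No reason is given for handling dose 1 otherwise.

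**Working it through.** **Inputs from the documents.** The screening window is Day -14 to Day -1 (Section 4.1). There are 30 placebo subjects per Part, made up of 15 in each dose cohort (Section 9.3), and 180 subjects in Parts A and B (Section 9.1). Summaries are by part and treatment (Section 9.6). Interims are by cohort (Section 9.5).

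**Assumptions, not in the documents.** Weekly infection risk is 0.1% to 1%. The rise after infection is 16- to 64-fold. Antibody becomes detectable 7 to 14 days after infection. GMI is not defined in Section 3.2.2, and I take it to be relative to baseline, like GMFR.

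1. *Gap.* With no Day 0, Day -14 to Day 1 is 14 days and Day -1 to Day 1 is 1 day. The baseline sample is therefore 1 to 14 days old at dose 1, which matches the stated 14-day maximum.

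2. *Expected cases, if every subject had the full 14-day gap.* Weekly risk × 2 weeks × n:
   - 30 placebo subjects in a Part: 0.001 × 2 × 30 = 0.06, to 0.01 × 2 × 30 = 0.6
   - all 180 subjects: 0.001 × 2 × 180 = 0.36, to 0.01 × 2 × 180 = 3.6

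   These are upper figures, since real gaps run from 1 day and no allowance is made for the exposure exclusions.

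3. *Effect of one case on a group GMFR.* The group value is multiplied by fold^(1/n), if that subject would otherwise show no rise (a placebo subject):
   - n = 30: 16^(1/30) = 1.10; 64^(1/30) = 1.15
   - n = 15 (one cohort at its interim): 16^(1/15) = 1.20; 64^(1/15) = 1.32

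4. *Which endpoints use the baseline value.* GMFR, the T-cell change, the serostatus label and (on the assumption above) GMI use it. Post-dose GMT and the post-dose GMT ratio are built from titres at the visit. Seroconversion is detectability at the visit. A gap infection gives the same values for these three wherever the baseline draw sits. Baseline timing reaches them only through which serostatus subset a subject is placed in.

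5. *The gap compared with infections after dose 1.* Under a constant hazard, the gap's share of infection time from the baseline draw to Day t is gap/(gap + t - 1). For a 14-day gap this is 14/35 = 40% at Day 22, 14/56 = 25% at Day 43 and 14/378 = 3.7% at Day 365. For a 1-day gap it is 1/22 = 4.5% at Day 22 and 1/43 = 2.3% at Day 43.

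6. *What a Day 1 titre would catch.* With a lag of 7 to 14 days to detectable antibody, the share of infections in a 14-day gap already visible on Day 1 is (14 - 7)/14 = 50%, down to (14 - 14)/14 = 0%.

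**The case against.** The strongest reply is that little is at stake and much of it is already watched. Section 5.2 excludes exposed workers, known close contacts, group-care residents and people with recent acute illness from Parts A and B, and Table 1-1 rechecks eligibility on Day 1. Anti-N assays are reported unblinded throughout (Appendix C). Because the vaccine antigen is RBD-Fc, anti-N separates infection from vaccine response. There is a Day 15 swab and exposure-triggered testing (Section 7.6). Infections after Day 1 enter the endpoints in the same way. The study is descriptive, without significance testing.

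This narrows the problem to unrecognised infection and keeps it small. It does not remove it: the monitoring leads to PCR and follow-up, and no text in the document reviewed re-baselines, flags or sets aside an infected subject in the immunogenicity summaries. Section 9 defers data conventions to a separate SAP whose text is not in that document, so a rule there cannot be excluded.

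Two further objections stand and limit the remedy. The rationale in the Amendment 8 table says enrolment has ceased, so changing the schedule cannot alter Parts A and B. And a Day 1 titre misses infections that have not yet seroconverted.

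A reader might also infer that gap infections inflate the responder rate, by 1/15 or 1/30 per case. The seroconversion definition does not support this as a baseline fault: it makes no reference to baseline and expressly allows for natural infection in placebo subjects. The same count would arise with a Day 1 draw.

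**Conclusion.** The point holds as a modest design weakness. The immunogenicity baseline is 1 to 14 days old at dose 1, and an unrecognised infection in the gap enters GMFR, GMI and the T-cell change as a rise after vaccination, with the subject labelled seronegative.

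A reader might infer a systematic bias favouring vaccine. The design does not support that: randomization makes gap infections equally likely in each arm. What remains is inflated within-arm fold rise, easiest to see in placebo, and some misclassified serostatus.

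Under the assumed risks, at most 0.06 to 0.6 cases are expected per 30-subject placebo group. One case with the assumed rise would multiply that group's GMFR by 1.10 to 1.15, or by 1.20 to 1.32 in a 15-subject placebo cohort at a cohort-level interim. These sizes rest on assumed infection risk and fold rise. The timing of the draws does not. The case for acting is that the remedy is cheap.

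**What to change.** **Subjects already enrolled in Parts A and B.** List the days from baseline sample to dose 1. Repeat the GMFR, GMI and T-cell summaries as a sensitivity analysis without subjects who were anti-N negative at screening and become anti-N positive at Day 8 or Day 15, or who are RT-PCR positive by Day 15. This uses data already collected and costs only programming. It will also set aside some infections acquired just after dose 1, so it belongs beside the main summary and should not replace it.

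**Any further enrolment (Part C).** Part C is still listed, at up to 1000 subjects, with the exposure, close-contact and group-care exclusions lifted. In Table 1-1, move the screening mark for the ELISA, neutralizing/anti-RBD/anti-Fc, PBMC and future-research rows to Visit 1, pre-dose. Keep the screening serostatus and RT-PCR rows. In Section 9, define the immunogenicity baseline and the seronegative subset on the Day 1 pre-dose sample.

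The number of samples per enrolled subject is unchanged, and none of these are drawn from screen failures. The cost is a pre-dose draw with same-day PBMC processing on Day 1, as Day 22 already requires. Since a Day 1 titre still misses recent infections, the anti-N/RT-PCR sensitivity summary is needed in Part C as well.
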